2.6.3 Neurological examinations

Neurological examinations assessments will be collected at screening, Day 1/Week 0, Week 12, 26, 38, and 52 (or at withdrawal if withdrawn prematurely). They will include, but are not limited to the patient's mental status, posture, cranial nerves, motor system including muscle atrophy, tone and power, reflexes, sensory system, coordination, gait, and age-appropriate responses.

Neurological examinations will be classified as normal/abnormal findings. Frequency shift table will be provided.

2.6.4 Weight, height, BMI

The weight, height (standing height will be used for patients >2 years of age and supine height will be used for patients ≤ 2 years of age) and BMI will be collected at Screening and within

24 hours prior to every infusion visit from Day 1/Week 0 to Week 64 (or withdrawal if withdrawn prematurely).

BMI = weight in kilograms / (height in meters)²

For these three parameters, change from baseline, in addition to observed values, will be calculated and summarized for all scheduled visits by age group cohorts and overall.

Age-appropriate growth in height is a matter of efficacy; please see [Section 2.8.2](#) for analysis of height z-scores.

2.6.5 Clinical laboratory evaluations

Clinical laboratory data consists of blood analysis, including hematology, clinical chemistry, and urinalysis. Analysis of all safety laboratory parameters will be conducted by a central laboratory.

The following clinical laboratory evaluations will be assessed by the site as specified in Section 1.2 to 1.4 of the study protocol. The laboratory parameters will be classified as follows:

- Hematology: Complete blood count including white blood cell (WBC, leukocytes) count, platelet count, hemoglobin, hematocrit, red blood cell (RBC, erythrocytes) count, WBC differentials (absolute and percentage of lymphocytes, monocytes, neutrophils, basophils, eosinophils, and (if applicable) abnormal cells). Platelet count and hemoglobin will also be analyzed as exploratory efficacy endpoints. See details in [Section 2.8.4](#).
- Clinical Chemistry: sodium, potassium, chloride, blood urea nitrogen (BUN), glucose, uric acid, calcium, phosphorus, magnesium, albumin, total protein, creatinine.
- Liver function tests: aspartate aminotransferase (AST), alanine aminotransferase (ALT), total bilirubin, direct bilirubin and alkaline phosphatase (AP).
- Coagulation: prothrombin time (Protome), partial thromboplastin time (PTT), international normalized ratio (INR) and D-dimer.
- Urinalysis: dipstick for pH, ketones, glucose, bilirubin, protein and blood.
- If female of child bearing potential, β -human chorionic gonadotropin (β -HCG) serum or urine test as appropriate per Protocol Sections 1.2 and 10.3.

Observed values, change from baseline and percent change from baseline to scheduled study time points will be summarized by age group cohorts and overall. By patient plots of hemoglobin, platelets, WBC, ALT, AST, total bilirubin will be provided. Summary plots over time will also be provided as needed.

Laboratory values will be classified as normal, above normal, or below normal based on normal ranges when provided by the laboratory. Shifts from baseline to scheduled time points, any time during the on-treatment period and the last available value, in the abnormality of hematology, liver function tests and clinical chemistry will be provided by age group cohorts and overall.

PCSA values for hematology, liver function tests and clinical chemistry (provided in [Section 2.11.5](#)) during the study (from first infusion start to last available observation) will be summarized by age group cohorts and overall. PCSA values for hematology, liver function test and clinical chemistry parameters will be provided in separate listings.

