### **9.1.8 Clinical laboratory evaluations**

The following hematology, chemistry, serology and urine analyses will be evaluated as indicated in [Section 1.2](#), [Section 1.3](#) and [Section 1.4](#).

- Hematology: complete blood count including white blood cell count, platelet count, hemoglobin, and hematocrit with absolute and percentage differential cell counts of lymphocytes, monocytes, neutrophils, basophils, eosinophils, and (if applicable) abnormal cells.
- Clinical chemistry: sodium, potassium, chloride, blood urea nitrogen, glucose, uric acid, calcium, phosphorus, magnesium, albumin, total protein, creatinine, AST, ALT, total bilirubin, direct bilirubin, AP.
- Coagulation: prothrombin time (Protome), partial thromboplastin time (PTT), INR, and D-dimer.
- Serology tests: hepatitis B antigen, hepatitis C antibodies, anti-human immunodeficiency virus-1 and anti-human immunodeficiency virus-2 antibodies.
- Urinalysis: dipstick for pH, ketones, glucose, bilirubin, protein and blood.
- If female of child bearing potential,  $\beta$ -hCG serum or urine test as appropriate per [Section 1.2](#) and [Section 10.3](#).

Analysis of all safety laboratory parameters will be conducted by a central laboratory. Procedures for handling and shipment of all central laboratory samples will be included in the information provided by the central laboratory. Specimens will be processed appropriately by the central laboratory facility and laboratory reports will be made available to the study investigator in a timely manner to assure appropriate clinical review.

Clinical laboratory values will be analyzed after conversion into standard international units. International units will be used in all listings and tables.

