#### 10.6.1.3.2.2 Acute phase reactions

Acute phase reactions observed in the phase 1 and phase 1b studies are considered as one type of IAR, specific to the infused olipudase alfa therapy (5, 6). From observations in both studies the APR reactions typically occurred within 12-72 hours following an infusion of olipudase alfa and were indicative of an inflammatory response. APRs were associated with elevations in hsCRP and changes acute phase reactants including, but not limited to, neutrophils, iron, ferritin, fibrinogen, D-dimer, transferrin, albumin, protime, and partial thromboplastin time. Patient AEs associated with the APR included (but are not limited to) pyrexia, nausea, vomiting, fatigue, and pain. Acute phase reaction is determined based on combined significant laboratory findings and clinical symptoms.

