### **Abnormalities analyses**

For parameters with laboratory ranges and/or abnormality criteria, an on-treatment analysis will be performed using all post-baseline assessments done during the on-treatment period, including rechecked values. Counts of patients with PCSAs will be provided in summary tables showing shifts from normal and abnormal baselines to post-baseline abnormalities, presented by age group the PCSA occurred in. The same type of summary tables will be provided for out-of-normal laboratory range values.

A listing of liver function data for patients who experienced at least one occurrence of ALT  $\geq 3$  ULN and at least one occurrence of total bilirubin  $\geq 2$  ULN during the study with at least one of them being post first infusion will be also provided.

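### SAP 2.6.5 leaves coagulation out of the normal-range shift tables that the protocol's general laboratory rule covers, and SAP 1.5 does not declare the change

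*SAP*

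**What the plan says.** **Protocol.** Section 9.1.8 puts coagulation among the clinical laboratory evaluations: prothrombin time, "partial thromboplastin time (PTT), INR, and D-dimer". It says that a central laboratory analyses all safety laboratory parameters. Section 11.4.2.2, under Abnormalities analyses, sets a rule by type of parameter and names no panel: "For parameters with laboratory ranges and/or abnormality criteria, an on-treatment analysis will be performed using all post-baseline assessments done during the on-treatment period". It describes tables of shifts from normal and abnormal baselines for PCSA values, and adds: "The same type of summary tables will be provided for out-of-normal laboratory range values". Section 10.6.1.3.2.2 lists the reactants that changed in acute phase reactions in the two adult studies, among them "neutrophils, iron, ferritin, fibrinogen, D-dimer, transferrin, albumin, protime, and partial thromboplastin time".

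**SAP.** Section 2.6.5 lists coagulation as a separate class (prothrombin time, "partial thromboplastin time (PTT), international normalized ratio (INR) and D-dimer") beside hematology, clinical chemistry and liver function tests. All classes get observed values, change and percent change by cohort and overall. Laboratory values are to be classified against the normal range where the laboratory gives one. The shift sentence then covers baseline to scheduled time points, any time on treatment and the last available value, but only "in the abnormality of hematology, liver function tests and clinical chemistry will be provided by age group cohorts and overall". The PCSA summary covers "PCSA values for hematology, liver function tests and clinical chemistry", and the listings have the same limit: "PCSA values for hematology, liver function test and clinical chemistry parameters will be provided in separate listings". Section 2.11.5 has no coagulation threshold.

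SAP 1.5 declares three departures from the protocol's statistical section: the hematology baseline, the listing of acute phase reactions and cytokine release syndrome, and the post-treatment period. Coagulation tables are not among them.

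**The concern.** Safety is the primary objective, and the analysis is descriptive. In such a trial the choice of tables is the analysis plan, so a table that the protocol's rule covers and the SAP omits without comment is an undeclared change to the primary analysis.

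The panel matters in this study. Three of its four tests are on the protocol's acute-phase list, and the protocol determines an acute phase reaction from laboratory findings and symptoms together. SAP 1.5 concedes that these reactions cannot be listed as such, because the e-CRF identified only infusion-associated reactions. Systematic laboratory tables are then one of the few ways to see the laboratory side of the reaction across all children. SAP 2.6.1.4 also makes bleeding an adverse event of other interest, so a reader of the report is likely to ask how many children left the normal coagulation range on treatment. No planned table answers that.

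**Working it through.** The plan gives no figure to reproduce: there is no sample-size calculation and no threshold for these tests. The check compares the texts, then asks what the planned outputs can tell a reader.

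**1. Does the protocol's rule reach coagulation?** The rule covers parameters with laboratory ranges. Coagulation is in the protocol 9.1.8 panel, which 11.4.2.2 governs. An out-of-range table needs only a reference range, not a PCSA threshold. So the rule reaches coagulation if the central laboratory supplies ranges for the four tests. The documents do not show those ranges; this is an assumption.

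**2. Can coagulation be read into the SAP's shift sentence?** No. Section 2.6.5 itself separates coagulation from clinical chemistry, and the sentence uses the section's own class names.

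| Blood panel in SAP 2.6.5 | Descriptive summary | Normal-range shift table | PCSA summary and listing |
|---|---|---|---|
| Hematology | yes | yes | yes |
| Clinical chemistry | yes | yes | yes |
| Liver function tests | yes | yes | yes |
| Coagulation | yes | **no** | no (no criterion defined) |

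**3. Are the data there to tabulate?** Counts from the protocol flow charts 1.3 and 1.4, treatment period:
- Adolescents: 5 quarterly visits × 3 samples (pre-infusion, 24 h, 48 h) + Week 64 = 16, as in Table 4.
- Ages 3 to <12: 5 × 2 (pre-infusion, 48 h; the 24 h sample is not required) + Week 64 = 11, as in Table 5.
- Age ≤2: one 48 h sample on Day 1 + 3 visits × 2 (Week 12 is exempt) + Week 64 = 8. Table 6 lists 11. The two should be reconciled, but the point does not depend on which is right.

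Every age group therefore has post-infusion coagulation values.

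**4. What can be recovered from the planned summary?** SAP section 2 gives n, mean, SD, median, minimum and maximum. Suppose that at one time point the median is within range and the maximum is above a common upper limit. Order the n values. At least one lies above the limit. If n is odd, at most (n − 1)/2 lie above; if n is even, at most n/2.
- n = 20 (planned minimum overall): 1 to 10 children, 5% to 50%.
- n = 7 (child cohort minimum, 3 + 4): 1 to 3 children, 14% to 43%.
- n = 4 (infant/early child minimum, 2 + 2): 1 to 2 children, 25% to 50%.
- n = 3 (adolescent minimum): exactly 1.

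Mean and SD narrow these ranges but do not in general fix the count. The summary also does not show whether the child was normal at baseline. Nor does it link time points: one child above the limit at each of five 48 h samples could be anything from 1 to 5 different children.

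**5. What would a hand count from listings take?** With 20 children, four tests and 8 to 16 samples each, 20 × 8 × 4 = 640 to 20 × 16 × 4 = 1,280 results. The SAP does not say that coagulation listings will flag out-of-range values, and the flagged listings in protocol 11.4.2.2 name hematology and biochemistry.

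**6. Do AE tables or narratives fill the gap?** Only in part. Protocol 10.6.2 records a laboratory abnormality as an AE only if it is symptomatic, needs treatment or consultation, changes dosing, is serious or is of special interest. SAP 2.10 has no coagulation trigger for a narrative. A child with an isolated out-of-range D-dimer or PTT and no symptoms could meet none of these conditions.

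**The case against.** The other side has a good deal to say, and much of it stands.

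- **The data are reported.** A reader might infer that individual coagulation abnormalities vanish into group means. The documents do not support that. Minimum and maximum are planned for values and changes, so a single extreme child shows as the maximum. SAP section 2 backs all tabulated data with listings.
- **There are patient-level routes.** Protocol 9.1.8 has the investigator grade every abnormal value and document clinically significant worsening as an AE. Such events are counted by patient in the TEAE tables. Bleeding has its own summary, and infusion-associated reactions get narratives. This stands, subject to the narrower recording conditions in protocol 10.6.2.
- **The missing PCSA output might look like a second departure.** It is not one. The protocol leaves PCSA thresholds to the sponsor and sets none for coagulation. Only the out-of-range tables are at issue.
- **The promise is generic.** The protocol does not name coagulation in its abnormality rule, and its flagged listings name only hematology and biochemistry. One could argue that its authors had only those panels in mind. But the rule is framed by whether a range exists, and if a narrower meaning was intended, SAP 1.5 is the place to say so.
- **An acute-phase role does not by itself earn a shift table.** hsCRP, iron and ferritin get descriptive summaries only. That is correct, but the protocol handles those safety biomarkers in a separate section (11.4.2.7) with descriptive statistics. Coagulation falls under the laboratory rule. The acute-phase list explains why the gap matters; it is not the source of the obligation.

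**Conclusion.** The point holds as an undeclared difference between protocol and SAP. One of four blood panels lacks the normal-range shift table that the protocol's general rule covers, and SAP 1.5 is silent. The loss is limited: coagulation results remain in descriptive statistics and listings, with some in AE records or narratives, but no output counts the children who moved from normal to abnormal. At the planned minimum of 20 children the count at a time point can be uncertain over 1 to 10, if the median is in range and the maximum is not.

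This rests on two assumptions: that the central laboratory supplies ranges for the four tests, and, for the counts in the working, that one upper limit applies to the children summarised together. Limits that vary by age would make the pooled summary harder still to read.

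The point does not show that a coagulation signal exists or was hidden, and no endpoint, data collection or patient management is affected. A reader might also infer that protocol 11.4.2.2 prescribes shift tables at 24 and 48 hours. It does not: it asks for shifts from baseline to post-baseline abnormality, using all on-treatment values. The time-point layout below comes from the SAP's own treatment of the other panels. The change is worth making because it is cheap and serves the primary safety objective.

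**What to change.** In SAP 2.6.5, add coagulation to the shift-table sentence, so that it covers hematology, coagulation, liver function tests and clinical chemistry on the same terms: each scheduled time point at which coagulation is collected for the age group, any time on treatment, and the last available value. Use the central-laboratory ranges, by age cohort and overall.

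Two details belong in the table specification:
- The 24 h column applies to adolescents only, because younger children have no required 24 h coagulation sample.
- Flow chart 1.4 shows no pre-infusion coagulation sample on Day 1 for children aged ≤2. Their baseline would be the screening value under the general rule in SAP 2.11.1 (latest value before first infusion); a footnote should say so.

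No PCSA threshold for coagulation needs to be added. If the sponsor prefers to leave the table out, SAP 1.5 should state the departure and the reason.

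The cost is a one-word edit to the sentence, the table notes above, and one more run of an existing table program. SAP 2.6.5 already plans to classify laboratory values against the normal range, so no new data are needed.

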### 7.2 EXCLUSION CRITERIA

Patients who have met all the inclusion criteria listed in [Section 7.1](#) will be screened for the following exclusion criteria:

- E 01. The patient has received an investigational drug within the 30 days before study enrollment.
- E 02. The patient has any of the following medical conditions:
  - a) An active, serious, intercurrent illness;
  - b) Active hepatitis B or hepatitis C infection;

- c) Infection with human immunodeficiency virus (HIV);
- d) Cirrhosis (determined by clinical evaluation);
- e) Significant cardiac disease (eg, clinically significant arrhythmia, moderate or severe pulmonary hypertension or valvular dysfunction, or <40% left ventricular ejection fraction by echocardiogram);
- f) Malignancy diagnosed within the previous 5 years (except basal cell carcinoma);
- g) Any other extenuating circumstance that can significantly interfere with study compliance, including all prescribed evaluations and follow-up activities.

- E 03. The patient has acute or rapidly progressive neurological abnormalities.
- E 04. The patient is homozygous for *SMPD1* gene mutations R496L, L302P, and fs330 or any combination of these 3 mutations.
- E 05. The patient has delayed gross motor skills.
- E 06. The patient has had a major organ transplant (eg, bone marrow, liver).
- E 07. The patient requires use of invasive ventilatory support.
- E 08. The patient requires use of noninvasive ventilatory support while awake and for >12 hours a day.
- E 09. The patient, in the investigator's opinion, is unable to adhere to the requirements of the study.
- E 10. The patient has a platelet count <60 × 10^3/µL (based on the average of 2 screening samples obtained greater than 24 hours apart).
- E 11. The patient has alanine aminotransferase or aspartate aminotransferase >250 IU/L or total bilirubin >1.5 mg/dL.
- E 12. The patient has an international normalized ratio (INR) >1.5.
- E 13. The patient is unwilling or unable to abstain from ingesting alcohol the day before through 3 days after each infusion of olipudase alfa during the treatment period. Measuring alcohol concentration in blood is not required.
- E 14. The patient is scheduled during the study for in-patient hospitalization including elective surgery.
- E 15. The patient requires medication(s) that may decrease olipudase alfa activity (eg, fluoxetine, chlorpromazine; tricyclic antidepressants [eg, imipramine, or desipramine]).
- E 16. The patient is breast-feeding.

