##### **Abnormality analysis**

For all parameters, an “on-treatment” analysis will be performed using all post-baseline assessments done during the on-treatment period, including rechecked values. Counts of patients with post-baseline PCSAs will be provided in summary tables regardless of the normal or abnormal status of the baseline by age group.

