2.6 ANALYSIS OF SAFETY DATA

Safety endpoints include data pertaining to the safety and tolerability of olipudase alfa: assessment of adverse events (AEs)/treatment-emergent adverse events (TEAEs), including AESIs (eg, infusion-associated reactions (IARs), symptomatic overdose, etc.); physical examinations; neurological examinations; clinical laboratory evaluations; vital sign measurements; ECGs; Doppler echocardiography; liver ultrasound Doppler; safety biomarkers; and immune response assessments. For laboratory endpoints, the summaries will use both the international system of units (SI) and US conventional units; figures will use the international system of units (SI); data listings will provide the results in original units as well as in standard units, where applicable.

All the safety analyses will be performed using the safety population. Patients will be summarized and displayed by age group cohorts and overall. Safety data will be reported up to and including the time of treatment withdrawal, and follow-up for AEs, where applicable. The baseline value is the last available value before the first infusion of olipudase alfa, except for white blood cell count, platelet count, hemoglobin and possibly ECG parameters. For complete definition of baseline, refer to [Section 2.11.1](#).

For all safety data, the observation period will be divided into 2 segments:

- The **pretreatment period** is defined as the time between when the patient gives informed consent and the start of the first infusion (excluded).
- The **on-treatment period** is defined as the time from the start of the first infusion (included) till the end of the study.

The following definitions regarding potentially clinically significant abnormality (PCSA) will be applied to laboratory parameters, vital signs and ECG:

The PCSA values are defined as abnormal values considered medically important by the sponsor according to predefined criteria/thresholds based on literature review and defined by the sponsor for clinical laboratory tests, vital signs, and ECG. These values are provided in [Section 2.11.5](#).

- PCSA criteria will determine which patients had at least 1 PCSA taking into account all evaluations performed, including unscheduled or repeated evaluations.
- Before determining a value as PCSA, the value will be rounded to the precision that the PCSA criterion is defined.

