2.11.5 Potentially clinically significant abnormalities (PCSA) criteria

In the safety data analysis, patients included in the PCSA analysis for a given parameter will be defined as subjects:

- Exposed to study treatment,
- With at least one parameter result after study treatment administration, and,
- With available laboratory limits when required for analysis.

Liver function tests

ALT	> 3 ULN By distribution analysis: > 3 ULN > 5 ULN > 10 ULN > 20 ULN
AST	> 3 ULN By distribution analysis: > 3 ULN > 5 ULN > 10 ULN > 20 ULN
Alkaline phosphatase	> 1.5 ULN
Total bilirubin	>= 1.3 ULN
ALT and total bilirubin	ALT > 3 ULN and total bilirubin > 2 ULN

Hematology

WBC	Birth/0 to 27 days old (Neonates)	<4.0 GIGA/L >25.0 GIGA/L
	28 days/1 month to 23 months old (Infants)	<4.0 GIGA/L >20.0 GIGA/L
	24 months/2 years to <6 years old (Children)	<3.0 GIGA/L >16.0 GIGA/L
	6 to <12 years old (Children)	<5.0 GIGA/L >17.0 GIGA/L
	12 to 16/18 years old (Adolescents)	<4.5 GIGA/L >13.5 GIGA/L
Lymphocytes	Birth/0 to 27 days old (Neonates)	<1.2 GIGA/L >17.0 GIGA/L
	28 days/1 month to 23 months old (Infants)	<2.0 GIGA/L >13.5 GIGA/L
	24 months/2 years to <6 years old (Children)	<1.0 GIGA/L >9.5 GIGA/L
	6 to <12 years old (Children)	<1.0 GIGA/L >8.0 GIGA/L
	12 to 16/18 years old (Adolescents)	<0.6 GIGA/L >6.0 GIGA/L

Neutrophils	Birth/0 to 27 days old (Neonates)	<4.0 GIGA/L (1 day old) <1.5 GIGA/L (2 – 7 days old) <1.25 GIGA/L (>7 day – 1 month old) >1 ULN
	28 days/1 month to 23 months old (Infants)	<1.0 GIGA/L (1 – 3 months) <1.2 GIGA/L (3 – 24 months) >1 ULN
	24 months/2 years to <6 years old (Children)	<1.2 GIGA/L >1 ULN
	6 to <12 years old (Children)	<1.2 GIGA/L >1 ULN
	12 to 16/18 years old (Adolescents)	<1.2 GIGA/L >1 ULN
Eosinophils	All age ranges	>0.5 GIGA/L Or >ULN if ULN \geq 0.5 GIGA/L
Hemoglobin	Birth/0 to 27 days old (Neonates)	<12.0 g/dL and 20% decrease from baseline, or decrease from baseline \geq 2 g/dL
	28 days/1 month to 23 months old (Infants)	<9.0 g/dL and 20% decrease from baseline, or decrease from baseline \geq 2 g/dL
	24 months/2 years to <16/18 years old (Children, Adolescents)	<10.0 g/dL and 20% decrease from baseline, or decrease from baseline \geq 2 g/dL
Hematocrit	Birth/0 to 27 days old (Neonates)	<0.39 l/l or 40% >0.61 l/l or 47%
	28 days/1 month to 23 months old (Infants)	<0.29 l/l or 29% >0.42 l/l or 42%
	24 months/2 years to <16/18 years old (Children, Adolescents)	<0.32 l/l or 32% >0.47 l/l or 47%

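### The SAP's laboratory PCSA table drops the protocol's split by baseline status without declaring it, so values already abnormal at entry are counted without baseline context

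*SAP*

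**What the plan says.** Protocol section 11.4.2.2, under Abnormalities analyses, says: "Counts of patients with PCSAs will be provided in summary tables showing shifts from normal and abnormal baselines to post-baseline abnormalities". It then adds: "The same type of summary tables will be provided for out-of-normal laboratory range values". The protocol therefore asks for two laboratory tables, both arranged by baseline status. For vital signs and ECG (sections 11.4.2.3 and 11.4.2.4) it chooses the opposite layout: "Counts of patients with post-baseline PCSAs will be provided in summary tables regardless of the normal or abnormal status of the baseline by age group".

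SAP section 2.6.5 keeps the out-of-range table, with shifts from baseline among normal, above normal and below normal. For the other table it says that PCSA values for hematology, liver function tests and clinical chemistry "during the study (from first infusion start to last available observation) will be summarized by age group cohorts and overall". Sections 2.6.6 and 2.6.7 use almost the same words for vital signs and ECG. The general rule in section 2.6 is: "PCSA criteria will determine which patients had at least 1 PCSA taking into account all evaluations performed, including unscheduled or repeated evaluations". Section 2.11.5 requires exposure, laboratory limits where needed, and a post-treatment result ("With at least one parameter result after study treatment administration, and"), but no baseline value.

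SAP section 1.5 lists three departures from the protocol's statistical section: the baseline for white cells, platelets and hemoglobin; the listing of acute phase reactions and cytokine release syndrome; and the removal of the post-treatment period. The laboratory PCSA layout is not among them.

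**The concern.** Safety is the primary endpoint and the study has one arm, so each patient's own baseline is the internal reference for laboratory change. The protocol names liver dysfunction as a feature of the disease (section 4.1). It also warns that laboratory values may lie outside the normal range because of the disease (section 9.1.8). Eligibility leaves room for this. The patient is excluded only under this criterion: "The patient has alanine aminotransferase or aspartate aminotransferase >250 IU/L or total bilirubin >1.5 mg/dL".

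A PCSA count taken from the first infusion onward, with no baseline column, mixes two groups: patients whose values crossed the limit on treatment, and patients who were beyond it at entry and stayed there, even while improving. A reader of that table cannot tell them apart.

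**Working it through.** The plan gives no figure to reproduce. The check has two parts: can a patient meet a PCSA limit at entry, and do the retained outputs identify that patient?

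**Inputs**
- ALT and AST PCSA: above 3 ULN, also tabulated at above 5, 10 and 20 ULN, with no baseline term. Total bilirubin PCSA: 1.3 ULN or more (SAP 2.11.5).
- Entry ceilings: 250 IU/L for ALT and AST, 1.5 mg/dL for total bilirubin (Protocol 7.2).
- At least 20 patients. Cohort minimums: 3 adolescents, 3 + 4 = 7 children, 2 + 2 = 4 infants/early children (Protocol 11.1).
- ULN: not in the documents. Assumed 30 to 60 IU/L for ALT and AST.

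**1. Can a patient enter above the limit?** 250 exceeds 3 × ULN when ULN < 250/3 = 83.3 IU/L, and exceeds 5 × ULN when ULN < 250/5 = 50 IU/L.

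| Assumed ULN (IU/L) | 3 ULN (IU/L) | Highest eligible entry, 250/ULN |
|---|---|---|
| 30 | 90 | 8.3 ULN |
| 40 | 120 | 6.25 ULN |
| 50 | 150 | 5.0 ULN |
| 60 | 180 | 4.2 ULN |

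For bilirubin, entry at or beyond the PCSA limit is possible when ULN ≤ 1.5/1.3 = 1.15 mg/dL.

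**2. Which criteria are affected?** In SAP 2.11.5 the hemoglobin and low-platelet criteria contain a decrease from baseline. The other hematology, liver and chemistry criteria do not. For high neutrophils the PCSA limit is the ULN itself, so the retained normal-range shift already shows the change.

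**3. Does the retained shift table separate the cases?** Take ULN = 40 IU/L and two invented patients.
- Patient A: ALT 220 to 130 IU/L, that is 5.5 to 3.25 ULN, a fall of 1 − 130/220 = 41%.
- Patient B: ALT 44 to 128 IU/L, that is 1.1 to 3.2 ULN, or 128/44 = 2.9 times baseline, with no symptoms or eosinophilia and stable bilirubin and alkaline phosphatase.

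Both count as PCSA above 3 ULN. Both are above normal before and after in the shift table. Neither meets a numerical liver AESI (adverse event of special interest) criterion in SAP 2.6.1.3: A has improved, and B is below 3 × 44 = 132 IU/L and lacks the conditions of the other two criteria. The protocol's own split would also put both in the abnormal-baseline row.

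**4. What do the liver AESI criteria catch?** If baseline ALT ≤ ULN and a later value exceeds 3 ULN, that value exceeds 3 × baseline and ULN, so the first criterion is met. For ALT and AST, every PCSA from a normal baseline is therefore identifiable through the AESI criteria, and the gap lies among abnormal baselines. Bilirubin differs: a move from 1.0 to 1.3 ULN is a PCSA at 1.3 times baseline, below both the 3-fold and the 1.5-fold criteria. There the protocol's normal/abnormal split carries information of its own.

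**5. Weight of one patient.** 1/20 = 5.0 percentage points overall. At the cohort minimums it is 1/3 = 33.3, 1/7 = 14.3 and 1/4 = 25.0 points. The minimums sum to 14, so with 20 or more patients not all cohorts can be that small.

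**The case against.** The strongest reply is that the SAP uses baseline in many other places. It plans change and percent change from baseline, by-patient plots of ALT, AST and total bilirubin (2.6.5), liver criteria relative to baseline (2.6.1.3), a by-patient listing of potential quantifiable dose-limiting toxicities (2.6.1.8), and narratives (2.10). With about 20 patients, a careful reader can find out who worsened. This stands, and it confines the problem to one categorical summary.

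A second reply is that section 2.6.5 is merely terse: it does not say that baseline is ignored. That is possible. However, its wording matches what the SAP uses for vital signs and ECG, where the protocol expressly sets baseline aside, so the omission is the more natural reading. Section 1.6 has redacted items, but it compares SAP versions. Departures from the protocol belong in section 1.5, which shows no redaction.

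A reader might also infer several stronger points that the documents do not support:
- That all laboratory PCSAs ignore baseline. Hemoglobin and low platelets do not.
- That the protocol would have left these patients out. It would count them too, in an abnormal-baseline row. What is lost is context, not an exclusion.
- That everyone entering above 3 ULN is counted. A value after infusion must also exceed 3 ULN.
- That the inflation can be stated as a rate. Without a baseline distribution, any proportion would be invented.

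**Conclusion.** The point holds in limited form. The SAP omits a baseline classification that the protocol requires for laboratory PCSA counts, and it does not declare the omission. For criteria with no baseline term, the resulting table can count a pre-existing or even improving abnormality alongside one that arose on treatment.

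For ALT and AST this is possible at any ULN below 83.3 IU/L. Each such patient adds 5.0 percentage points in a study of 20. How many patients are affected cannot be computed. The conclusion rests on reading section 2.6.5 as a plain count and on an assumed ULN for the multiples shown. It does not mean that the plan is unable to detect liver worsening, because the other outputs can show it patient by patient. It means that the PCSA table alone should not be read as treatment-emergent.

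**What to change.** In SAP section 2.6.5, state that each hematology, liver function and chemistry PCSA table is presented by baseline status (normal, abnormal, missing), as Protocol section 11.4.2.2 requires. If the sponsor prefers the plain count, section 1.5 should declare and justify it.

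As a refinement beyond the protocol, divide abnormal baseline into PCSA absent and PCSA present. For ALT and AST, cross-tabulate baseline category against worst on-treatment category, using the SAP's own cut-points: up to 3, above 3, above 5, above 10 and above 20 ULN, as non-overlapping bands. The refinement is needed because a normal/abnormal split cannot distinguish entry at 1.1 ULN from entry at 5 ULN.

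The cost is a few sentences and a revised table shell. Cells will be small, especially by cohort, so counts should be shown with the percentages. No new data are needed.
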